– **Our primary hypothesis** is that current use of highly effective contraception (includes *sterilization, subdermal implant, intrauterine device, injectable, pill, patch, or ring*) will be greater at 1-month post-enrollment among women recruited during the intervention period (i.e., “SexHealth Mobile”) compared to those recruited during the usual care period. We will also compare current use and discontinuation rates at 2-weeks and 3-months among all participants.

1.2 Our secondary objective is to explore intervention feasibility.

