3.0 Study Endpoints

- 3.1 Primary Endpoint: Study will end data collection when the estimated sample size has been enrolled to show statistically significant effects for women with any type of SUD, including those with OUD.

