Our multi-disciplinary team developed the assessment tools, based on national surveys and a review of the pertinent literature including validated items where applicable. At baseline, we will assess for high-risk sexual behaviors, substance use, relationship status, health care access and utilization, health history (e.g., pregnancies, mental health), and demographic information. Follow-up surveys will assess for contraception use (including condoms), healthcare utilization, health history, intervention satisfaction and feasibility.

Baseline information will be collected directly from participants on an iPad recorded on REDCap. Follow-up surveys will be completed after enrollment and recorded in REDCap.

See our measure tools to know what demographic, baseline, and follow-up data will be collected.

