18.0 Data Management and Confidentiality

18.1 Statistical Methods:

Demographic variables collect from both control and intervention participants will be summarized and compared. Categorical variables will be reported as frequencies and percentages; whereas, continuous variables will be reported as means with standard deviations or medians with interquartile ranges depending on which is more appropriate. Fidelity will be assessed through analyzing recordings using a checklist developed for the delivery of the training. Differences between groups regarding the usage of highly effective contraception at 1-month post enrollment will be compared using a Fisher's Exact Test. We will also compare contraception usage at 2-weeks and 3-months post enrollment. Baseline and follow-up survey data will also be summarized and compared. Likert-scale items will be compared using Wilcoxon Mann Whitney tests. To assess the primary outcome, logistic regression models will be fit to investigate potential predictors for utilizing highly effective contraception at the post enrollment time points.

All statistical tests will be conducted at the alpha = 0.05 level. Statistical analysis will be done using The SAS software v 9.4 (Copyright, SAS Institute Inc. SAS and all other SAS Institute Inc. product or service names are registered trademarks or trademarks of SAS Institute Inc., Cary, NC, USA) and R statistical software (R Core Team (2015). R: A language and environment for statistical computing. R Foundation for Statistical Computing, Vienna, Austria. URL <http://www.R-project.org/>).

18.2 Multiplicity:

We are powered to test our primary hypothesis for both the entire sample as well as the subsample of women with OUD in both the usual care and interventional groups. Survey responses collected at baseline and follow-up will have multiple items which will be compared and adjusted for multiple comparisons using a Bonferroni correction.

18.3 Power/Sample Size:

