This n is based on Fisher's exact test assuming uptake of 20% in the baseline period and 76% in the intervention period (based on studies showing uptake of point-of-care contraception among active drug users [66%] and women in recovery [85%]). Assuming 90% power and an error probability of $\alpha = 0.05$, this calculation gives us starting sample size of 32. Because we want to show statistically significant effects for both women with any type of SUD including those with OUD, and estimating that 30% of the study population will have OUD (according to estimates from our partner sites), we want to finish with 107 women with in total (30% of this is 32). To protect against attrition with this highly transient population, we will oversample our total by 50%, bringing our total N=160 (107x1.5).

18.4 Data Management:

To minimize risk of possible breach of confidentiality, data will be entered and stored into REDCap by study staff. Data will be stored on a CM secure network via CM encrypted password protected tablet and laptop. Participants will be assigned a unique REDCap ID number for management of their data collection. Online consent forms will minimize risk of transporting PHI back to CM from the recruitment sites.

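### Does Section 18.2 need a rule for the case where the whole sample and the OUD subsample give different answers?

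*Combined protocol and SAP*

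**What the plan says.** Section 1.1 states one primary hypothesis: use of highly effective contraception "will be greater at 1-month post-enrollment among women recruited during the intervention period" than among those recruited under usual care. It does not mention OUD. Section 18.1 assigns one test to this outcome, Fisher's exact test at 1 month, and adds: "All statistical tests will be conducted at the alpha = 0.05 level". It lists no separate OUD analysis.

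The OUD subsample enters in three places:

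- Section 18.2: "We are powered to test our primary hypothesis for both the entire sample as well as the subsample of women with OUD".
- Section 18.3, explaining why 32 women become 107: "Because we want to show statistically significant effects for both women with any type of SUD including those with OUD".
- Section 3.1, where data collection ends once enough women are enrolled "to show statistically significant effects for women with any type of SUD, including those with OUD".

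The only adjustment in Section 18.2 is for survey responses, which "will have multiple items which will be compared and adjusted for multiple comparisons using a Bonferroni correction".

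**The concern.** A section headed Multiplicity puts the primary hypothesis to two nested populations and, for that pair, speaks only of power. Power neither controls false positives nor defines success. If the whole sample is significant and the OUD subsample is not, Section 1.1 suggests that the hypothesis is supported, while the wording of Section 18.3 could be read as asking for both. With no rule, the reading could be chosen after the data are seen. If a result in either population could be claimed, two tests at 0.05 might also push the overall error above 5%.

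A smaller doubt concerns the Bonferroni sentence. Section 5.4 collects contraception use by follow-up survey, so the primary outcome could be thought to fall under that correction.

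**Working it through.** **Inputs.** Rates of 20% and 76%, 90% power, alpha 0.05, starting size 32, OUD share 30%, 107 evaluable women and 160 enrolled, all from Section 18.3; equal periods from Section 1.0. The plan does not say whether tests are one- or two-sided, so both are shown.

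**The plan's own figure.** With mean rate 0.48 and difference d = 0.56, the normal formula per period is

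n′ = [z_α √(2 × 0.48 × 0.52) + 1.282 √(0.20 × 0.80 + 0.76 × 0.24)]² / 0.56²

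and the continuity correction is n = (n′/4) [1 + √(1 + 4/(n′d))]².

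- One-sided (z_α = 1.645): n′ = 11.7, corrected 15.02, so 16 per period and 32 in total. This matches.
- Two-sided (z_α = 1.960): 15 per period (30) uncorrected, 18 per period (36) corrected.

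Then 32/0.30 = 106.7, or 107, and 107 × 1.5 = 160.5, given as 160. Exact Fisher power with 16 v 16 is 92.6% one-sided and 85.4% two-sided.

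**Chance of a split.** Simulation of 200,000 trials per row, Fisher's test at 0.05 in each population, OUD count random with a 30% share in each period, same rates in women with and without OUD:

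| Rates | Whole sample v total | OUD power, 1-/2-sided | Whole sample only, 1-/2-sided |
|---|---|---|---|
| 20% v 76% | 53 v 54 | 90.4% / 86.8% | 9.6% / 13.2% |
| 20% v 66% | 53 v 54 | 75.5% / 69.3% | 24.5% / 30.6% |
| 20% v 85% | 53 v 54 | 97.3% / 95.9% | 2.7% / 4.1% |
| 20% v 76% | 80 v 80 | – | 1.6% / 2.7% |

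The second column gives women per period. At 20% v 76% the whole-sample test is significant in effectively every trial, so the split is one minus the OUD power: 100% − 90.4% = 9.6%. Any subgroup with about 90% power has this property. The 66% row applies to every woman the source rate for active drug users; the planned 76% is about the midpoint of the two source rates, (66 + 85)/2 = 75.5.

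**What an order of testing would change.** Testing OUD only after a significant whole-sample result removes just the trials where OUD alone is significant. At 20% v 66%, the least favourable row, these are 0.0000 of trials one-sided and 0.0001 two-sided.

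**False positives.** The correlation between the nested tests is √0.30 = 0.55. If a result in either population counted, the nominal error would be 8.9% two-sided. Fisher's test is conservative at these sizes. With fixed OUD counts and a common rate of 20%, the two-sided sizes at 107 women are 1.7% (OUD) and 3.5% (whole), and 4.8% for either. Over assumed common rates of 20% to 50%, fixed or random OUD counts, and 107 or 160 women, the chance that either is significant is 4.2% to 5.7% one-sided and 4.9% to 6.3% two-sided; a repeat run reached about 6.6%.

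If only women without OUD benefit (20% v 76%) and OUD women have a common rate of 20% to 50% in both periods, a false OUD claim under ordered or joint testing occurs in 1.7% to 2.7% of trials at 107 women and 2.4% to 3.5% at 160.

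**The Bonferroni sentence.** Section 18.1 first gives the 1-month outcome its Fisher test, then the other two time points, and only then says that survey data will also be compared. Section 18.2 follows the same order: primary hypothesis, then survey items. Read together, the correction covers the other items.

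**The case for a change.** The best case for a change is that the OUD test is no casual subgroup look. It sets the sample size, raising the evaluable target from 32 to 107, yet Section 18.1 lists no OUD analysis and nothing gives its result a role. A split in about one trial in ten, or in a quarter or more at the low source rate, is realistic. The relevant size is 107, since Section 1.0 counts the 160 as evaluable at the index visit while the outcome is measured at 1 month. A sentence naming the rule would cost nothing and leave every sample size alone.

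The gap stands, and so do the figures. What does not stand is that the plan holds two competing success rules. The wish for both results explains a sample size in Section 18.3, and Section 3.1 sets the end of data collection; neither defines success. Sections 4.1 and 18.2 treat women with OUD as part of the larger group. A split also has a plain report: an effect shown over all women, and not shown separately in those with OUD. Ordered testing would give exactly that report. Requiring both would change the label on the result, not the estimates or the p-values.

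**Conclusion.** This is missing detail that an analyst would fill sensibly, and filling it in advance would gain almost nothing. Followed as written, the plan gives a sound whole-sample test at 0.05 and a separate OUD result, itself a valid exact test at 0.05. A split has a chance of about 10% one-sided or 13% two-sided at 20% v 76% with 107 women, and about 2% to 3% with 160. Testing in order would alter a conclusion in about 0% of trials. An overall error of about 4% to 7% arises only under an either-population claim that the plan does not make.

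The conclusion rests on a 30% OUD share in each period, equal rates in women with and without OUD for the split figures, and assumed common rates of 20% to 50% for the error figures. It also takes the Section 1.1 hypothesis as the primary claim, which is the natural reading.

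### Section 18.2 corrects the survey items with single-step Bonferroni; Holm's step-down procedure on the same family keeps the same error control and never rejects less

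*Combined protocol and SAP*

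**What the plan says.** Section 18.2 (Multiplicity) states: "Survey responses collected at baseline and follow-up will have multiple items", and these are to be "compared and adjusted for multiple comparisons using a Bonferroni correction". It names no step-down or other sequential version. It also does not say how many items there are, or whether they form one family or several.

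Section 18.1 sets the level, "All statistical tests will be conducted at the alpha = 0.05 level", without saying whether tests are one- or two-sided. For the ordinal items it says: "Likert-scale items will be compared using Wilcoxon Mann Whitney tests".

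The primary comparison is separate. In 18.1, "usage of highly effective contraception at 1-month post enrollment will be compared using a Fisher's Exact Test", and 18.2 does not list it among the items to be Bonferroni-adjusted.

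Section 5.4 says the follow-up surveys cover contraception use, healthcare utilization, health history, satisfaction and feasibility. It refers to measure tools that are not part of the documents. Exploring feasibility is the secondary objective (section 1.2).

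**The concern.** Single-step Bonferroni holds every item to 0.05/m, where m is the number of items, however many other items have already been shown to differ. Once an item has been rejected, the remaining items no longer need so strict a threshold to keep family-wise error at 0.05. Holm's procedure uses that slack and needs no assumption that Bonferroni does not.

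What is at stake is modest: some true differences in secondary survey items may be missed that an equally strict procedure would have found. The survey items bear on the secondary objective, and the sample size was not set for them. The plan wants to finish with 107 women, so per-item power after correction may be limited.

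**Working it through.** **Inputs from the documents.** Alpha 0.05 (18.1); plain Bonferroni for the survey items (18.2); 107 women at the end of the study (18.3). The plan gives no item count, per-item alpha or power for the survey items, so it has no figure to reproduce.

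**Inputs assumed.** The 107 women split 53 v 54. Tests are two-sided z tests, as an approximation to the planned tests. Items have equal correlation of 0.3. The number of items (m), the number with a true effect (k) and the effect size are varied.

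**Step 1: the two rules.** Order the p-values from smallest to largest.
- Bonferroni rejects an item if p ≤ 0.05/m.
- Holm rejects the i-th smallest if p ≤ 0.05/(m − i + 1), and stops at the first failure.

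With m = 10, Bonferroni uses 0.05/10 = 0.005 for every item. Holm uses 0.05/10 = 0.005, then 0.05/9 = 0.00556, then 0.05/8 = 0.00625, and so on up to 0.05/1 = 0.05. Every Holm threshold is at least 0.05/m, so Holm rejects whatever Bonferroni rejects. If the smallest p-value is below 0.005 and the second lies between 0.005 and 0.00556, Holm rejects both and Bonferroni only the first.

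**Step 2: error control.** Suppose m0 items have no true difference. When Holm first rejects one of them, all m0 are still in the running, so m − i + 1 ≥ m0 and that p-value is at most 0.05/m0. The chance that any of the m0 p-values is that small is at most m0 × 0.05/m0 = 0.05, whatever the dependence between items.

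**Step 3: the planned method is valid.** For m independent items with no true effects, Bonferroni's family-wise error is 1 − (1 − 0.05/m)^m. This is 0.0490, 0.0489, 0.0488 and 0.0488 for m = 5, 10, 20 and 40.

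**Step 4: size of the gain.** The standard error of a standardised difference is √(1/53 + 1/54) = 0.1934. A 0.7 SD effect therefore gives a mean z of 0.7/0.1934 = 3.62. The Bonferroni critical value for m = 10 is 2.807, so power per item is Φ(3.62 − 2.807) = 79.2%, in line with the simulated 79.1%. Holm's power depends on the other items and was simulated.

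| Items (m) | True effects (k) | Effect | Bonferroni | Holm | Gain (points) |
|---|---|---|---|---|---|
| 10 | 8 | 0.7 SD | 79.1% | 86.1% | 7.0 |
| 20 | 10 | 0.6 SD | 53.0% | 56.5% | 3.5 |
| 20 | 5 | 0.6 SD | 53.2% | 54.6% | 1.4 |
| 20 | 4 | 0.5 SD | 33.3% | 34.0% | 0.7 |
| 10 | 2 | 0.5 SD | 41.5% | 42.1% | 0.6 |
| 10 | 5 | 0.3 SD | 10.6% | 11.1% | 0.5 |
| 20 | 4 | 0.3 SD | 7.1% | 7.2% | 0.1 |

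No Bonferroni rejection was lost under Holm in any run, and Holm's family-wise error stayed below 0.05 throughout. Holm found at least one extra item in about 43%, 29% and 7% of simulated trials in the first three rows, and in no more than about 3% in the last four.

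**Step 5: a second set of assumptions.** Take independent items, each true effect having 80% power before correction. Bonferroni v Holm:
- m = 10: 50.1% v 50.9% with 2 true effects, 49.7% v 52.9% with 5, and 49.7% v 60.9% with all 10.
- m = 20: 41.3% v 42.1% with 4 true effects, 41.2% v 43.9% with 10, and 41.2% v 49.3% with all 20.

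The pattern is the same: about 1 point when a fifth of the items differ, about 3 when half do, and 8 to 11 when all do.

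**The case against.** The strongest reply is that Bonferroni is prespecified and valid. It does not inflate error or bias any estimate, and it affects neither the primary comparison nor the sample size. The items concerned are secondary. All of that stands, and it is why this is an optional improvement and not a correction of an error.

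The size of the gain is also open to challenge. The item count, effect sizes, correlation and share of items that truly differ are all absent from the documents. The 7-point case needs 8 of 10 items to differ by 0.7 SD, which is favourable to Holm; with few or small effects the gain almost vanishes. That stands too, and the range must be shown with its assumptions. It does not affect the dominance result, which holds for every m and every pattern of effects.

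Three stronger readings are tempting, and the documents do not support them.
- A reader might infer that the change should also create one family per follow-up time and leave baseline items out, at the same error rate. Section 18.2 names baseline and follow-up together and can be read as one family. On that reading, three families at 0.05 each would allow overall error of up to 3 × 0.05 = 0.15. The same-error-rate argument holds only if the family is left alone.
- A reader might infer that the change has no drawback at all. Bonferroni gives simple simultaneous confidence intervals at level 1 − 0.05/m, whereas intervals that match Holm's decisions are less simple. The drawback is small here, because the plan does not mention such intervals.
- A reader might infer that the plan will lose findings. It may in some datasets, but the documents cannot show how often.

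The plan also leaves the family undefined: which items, at which times, and how many. That gap is the same under either procedure, and naming Holm does not close it.

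**Conclusion.** The point holds as an efficiency improvement. On any given family, Holm gives the same guarantee of family-wise error at 0.05, under any dependence, and never rejects fewer items than the Bonferroni correction named in 18.2. This follows from the two rules and rests on no assumption about the data.

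The practical benefit does rest on assumptions. With 53 v 54 women and a correlation of 0.3, the gain in power per true effect is about 0 to 1 point when few items differ or effects are small, and about 7 points when 8 of 10 items differ by 0.7 SD. The plan as written is not wrong, and leaving it unchanged would not invalidate any conclusion.

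**What to change.** In section 18.2, name the Holm step-down procedure in place of the Bonferroni correction. Apply it to the same family of items that the sponsor intends for Bonferroni, with no change to that family. Make the change before the follow-up data are compared, since a switch made after results are seen would look data-driven.

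The cost is one phrase in the plan and no extra data. If the sponsor wants simultaneous confidence intervals for these items, it should weigh the simpler Bonferroni intervals against the added power. Sections 18.1 (primary test) and 18.3 (sample size) need no change on this account.

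### The 90% power stated in section 18.3 for 32 women with OUD matches a one-sided Fisher test that the plan never declares; two-sided, power is about 85-89% at near-equal splits

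*Combined protocol and SAP*

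**What the plan says.** Section 18.3 gives the test and rates: "This n is based on Fisher's exact test assuming uptake of 20% in the baseline period and 76% in the intervention period". It then sets the operating characteristics, "Assuming 90% power and an error probability of" 0.05, and concludes that "this calculation gives us starting sample size of 32". It takes 30% of the study population to have OUD and scales up so that the OUD subsample alone reaches that number: "we want to finish with 107 women with in total (30% of this is 32"). A 50% allowance for attrition takes 107 to 160.

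Section 18.1 describes the analysis: "Differences between groups regarding the usage of highly effective contraception at 1-month post enrollment will be compared" with Fisher's exact test, and "All statistical tests will be conducted at the alpha = 0.05 level". Section 18.2 adds: "We are powered to test our primary hypothesis for both the entire sample as well as the subsample of women with OUD".

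The primary hypothesis in the opening objectives is directional: use of highly effective contraception "will be greater at 1-month post-enrollment among women recruited during the intervention period". No section says whether the Fisher test is one-sided or two-sided.

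**The concern.** The OUD subsample sets the size of the whole study (32, then 107, then 160), so the 90% attached to 32 is the one power figure on which everything else rests. A comparison of differences between groups at alpha 0.05, with no side stated, would ordinarily be read as two-sided. On that reading 32 does not deliver the stated 90%.

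The missing word also matters for the result. At the plan's own rates and 32 completers, the chance that the OUD comparison is significant one-sided but not two-sided is 3.3% to 7.2% for splits from 14/18 to 18/14. For example, 5/16 under usual care v 11/16 under the intervention gives p = 0.038 one-sided and p = 0.076 two-sided. If the side is left open, that choice could be made after the data are seen.

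**Working it through.** **Inputs**
- Test: Fisher's exact test (18.1 and 18.3).
- Rates: p1 = 0.20 under usual care, p2 = 0.76 under the intervention (18.3).
- Alpha 0.05, side not stated (18.1, 18.3). Target power 90% (18.3).
- OUD completers: 0.30 × 107 = 32.1, so 32 is a total over both periods, not a number per period (18.3).
- Split of OUD women between periods: not fixed in the documents. The Study Summary plans 80 women per period overall, so 16/16 is the natural central assumption. Splits from 10/22 to 22/10 were also run.

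**Method.** Exact power by enumerating every possible table:

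Power = Σx Σy Bin(x; n1, 0.20) × Bin(y; n2, 0.76) × I[Fisher p(x, y) ≤ 0.05]

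Here x and y are the numbers using highly effective contraception out of n1 (usual care) and n2 (intervention).

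**Step 1: reproduce the plan's 32.** One-sided, equal periods:
- 15/15 (total 30): 89.7%
- 16/16 (total 32): 92.6%

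So 32 is the smallest equal-period total reaching 90% one-sided.

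**Step 2: the same total, two-sided.**

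| Usual care / intervention | Two-sided | One-sided |
|---|---|---|
| 10/22 | 81.9% | 85.6% |
| 11/21 | 83.1% | 88.7% |
| 12/20 | 84.7% | 90.9% |
| 13/19 | 87.7% | 90.3% |
| 14/18 | 87.3% | 92.2% |
| 15/17 | 89.2% | 92.5% |
| 16/16 | 85.4% | 92.6% |
| 17/15 | 88.2% | 92.8% |
| 18/14 | 87.3% | 92.6% |
| 19/13 | 88.1% | 90.1% |
| 20/12 | 85.4% | 91.0% |
| 21/11 | 83.4% | 88.2% |
| 22/10 | 83.2% | 85.5% |

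The two-sided maximum is 89.2%. Averaged over random 50:50 splits of 32, power is 86.8% two-sided and 91.4% one-sided.

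**Step 3: how far 32 is from a two-sided 90%.**
- Total 33: 90.6% (15/18), 90.8% (16/17), 91.1% (17/16), 90.7% (18/15)
- 17/17 (total 34): 89.2%
- 18/18 (total 36): 92.1%

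Power is not monotone in the total because Fisher's test is discrete.

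**Step 4: what the attrition allowance does.** The plan enrols 160 to finish with 107, a loss of 53/160 = 33%.
- 25% loss: 160 × 0.75 = 120 completers, and 120 × 0.30 = 36 with OUD. At 18/18, two-sided power is 92.1%.
- No loss: 160 × 0.30 = 48 with OUD. At 24/24, two-sided power is 97.7%.

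**Step 5: whole sample.** 107 completers split 53/54, two-sided: above 99.9%.

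**The case against.** The strongest reply is that the effect is small and partly an artefact. At near-equal splits the gap to 90% is about 1 to 5 points. One more woman, at 16/17, gives 90.8%. The low value at 16/16 partly reflects the discreteness of Fisher's test. The 30% OUD share is itself a site estimate: the binomial standard deviation of the OUD count among 107 is √(107 × 0.30 × 0.70) ≈ 4.7 women, more than the shortfall. Step 4 shows that the gap disappears if 25% rather than a third are lost. All of this stands, and it limits the weight of the point. It does not make the stated 90% correct at the planned 32 completers.

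A second reply is that the directional hypothesis implies a one-sided test. It may explain where 32 came from, but a directional hypothesis does not declare a rejection rule, and 18.1 speaks only of differences. If one-sided was meant, a sentence saying so settles the matter.

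A third is that another test fits: a two-sided uncorrected chi-square gives 92.8% at 16/16. Both 18.1 and 18.3, however, name Fisher's test.

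Three stronger readings are tempting, and none is supported:
- A reader might infer that section 18.2 is wrong to call the study powered for the OUD subsample. That section gives no power level, and 85-89% does not contradict it. The 90% appears only in 18.3.
- A reader might take 85-89% as the range for any split. It holds for 14/18 to 18/14; power is about 82-85% at 10/22 to 12/20.
- A reader might infer that declaring a one-sided test rescues 32 whatever the split. It does so from 12/20 to 20/12, but at 10/22, 11/21, 21/11 and 22/10 one-sided power is 85.5% to 88.7%.

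**Conclusion.** The point holds in a limited form. The 90% in section 18.3 for 32 OUD completers corresponds to a one-sided Fisher test that the plan does not declare. Read two-sided, the same 32 women give 85.4% at 16/16, about 85-89% at near-equal splits and somewhat less at uneven ones.

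This rests on the plan's rates of 20% and 76%, on exactly 32 OUD completers, and on rejection at p ≤ 0.05. It concerns the OUD subsample only. The size of the gap would not by itself justify changing the design. The point is worth fixing because this figure drives the total of 160 and because the decision rule for the OUD test is left open.

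**What to change.** Before the data are analysed:
- In 18.1 and 18.3, state that the 1-month Fisher test is two-sided at 0.05.
- In 18.3, restate OUD power at 32 completers as about 85% at 16/16 (about 85-89% for near-equal splits between periods, lower if more uneven).
- If a one-sided test was intended, declare that in 18.1 and 18.3 instead, and note that 32 then gives at least 90% for splits from 12/20 to 20/12.
- Section 18.2 need not change; a cross-reference to the restated figure is optional.

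The cost is a few words, with no extra enrolment and no effect on the power of the whole-sample test. The one downside of the two-sided option is that the stated OUD power becomes slightly less favourable.
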